Our participants will be middle-aged adults since objective sleep duration significantly correlates with age in an inverse manner. We will not exclude insomniacs with minor forms of anxiety or depression, i.e., dysthymic disorder, since these conditions are highly comorbid in chronic insomniacs (Buysse et al, 1993; Kales and Kales, 1984; Buysse et al, 1994a; Buysse et al 1994b). However, insomniacs with a current diagnosis of a major mental disorder, i.e., schizophrenia, major depression, will be excluded from the study because these conditions are associated with the primary outcome variables of this study. In addition, we will exclude subjects with morbid obesity (BMI > 39) because, at this level, obesity is frequently associated with frequent sleep pathology, i.e., apnea, EDS, and significant medical morbidity (Vgontzas et al, 1994; Vgontzas et al, 1998).

Participants with an apnea/hypopnea index (A/HI) > 5 or periodic limb movements > 5 per hour of sleep will be excluded from the study. Also, subjects with a primary disorder of EDS, e.g., narcolepsy, or subjects with a history of shift work or circadian disorder will be excluded from the study (Vgontzas and Kales, 1999; Roehrs et al, 2005; Boggild and Knutsson, 1999) (Table 2).

Table 2. Inclusion/exclusion criteria.

Inclusion	Exclusion
Chronic insomnia (RDC) with a duration \geq 1 year Objective short sleep duration (< 6h) BMI < 39 Age range: 30-60 Equal number of men and women	Major mental illness Substance abuse/dependence Sleep apnea (apnea/hypopnea index \geq 5) PLMD (periodic limb movements \geq 5) Objective normal sleep duration (\geq 6h) Primary disorders of EDS, i.e., narcolepsy Shift work or circadian disorders Diabetes, chronic renal failure, hepatic insufficiency, chronic heart failure Current use of hypnotics or sleep inducing sedative antidepressants

RDC = research diagnostic criteria; PLMD = periodic limb movements disorder

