Subjects treated for diabetes or suffering from chronic renal failure or hepatic insufficiency or chronic heart failure will be excluded from the study. Also, because of the known effects of steroids on sleep, subjects on those medications will be excluded from the study. A family history of diabetes will be recorded during the medical history and physical examination and controlled within our analyses. Also, the potential effects of other medications or substances, such as alcohol or smoking, will be controlled within our analyses. Subjects with a diagnosis of substance abuse or dependence will be excluded from the study due to the potential effects of these substances on sleep and metabolism. Patients should be free of hypnotic use or sedative antidepressants administered at bedtime to improve sleep for one month before entering the study. Finally, patients using psychotropic medications, i.e., SSRI, who do not meet the criteria for a current major psychiatric disorder, and have continuous complaints of insomnia, will be included in the study. This is because a large portion of insomniacs consist of depressed individuals whose depression improved but still they have complaints of chronic insomnia. Potential confounding effects of medication on some of the outcome measures, i.e., objective sleep duration, will be dealt with in the analysis

Women and Minority Inclusion – In this project, we will include middle-aged men and women 30- 60 because they represent the majority of patients with insomnia in the general and clinic population. Women who are pregnant or breastfeeding will not be enrolled in the study. We plan to recruit about 21% of subjects belonging in minority groups. The racial and ethnic distribution shown in the Targeted/Planned Enrollment Table reflects the general demographics of our region. Minorities will be recruited from our clinics as well as through advertisements in papers with large groups of minority readers, such as Harrisburg, PA and Lebanon, PA.

IRB Protocol No. 35933
Version Date: 11/10/2015

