6.0 Study Procedures

Screening phase

The subjects' diagnoses of insomnia and other sleep disorders will be established by a clinical sleep history conducted by a clinical psychiatrist or psychologist who practices sleep medicine. The subjects that meet the research diagnostic criteria (RDC) for insomnia will be included in the study (see Table 1). The subjects' sleep patterns will be assessed via a sleep diary and actigraphy (for two weeks) prior to their visit to the sleep lab. Each subject will be monitored continuously for eight hours for one night in the sleep unit of the GCRC according to standard techniques (Rechtschaffen and Kales, 1986; Iber et al, 2007.). The first night will serve as a screening night for the presence of sleep apnea or periodic limb movements, and an adaptation night to control for "first night" effects. Prior to or during their visit to the sleep unit, the participants will be assessed for psychiatric disorders using a Structured Clinical Interview for DSM-IV, the Mini International Neuropsychiatric Interview (MINI ; Sheehan et al, 2006).

Figure 1. Screening phase, randomization of patients with insomnia.

Randomized Clinical Trial of Trazodone vs. CBT

a. Baseline measures – Following the screening night, the subjects that will enter the randomized trial will be monitored in the sleep laboratory continuously for 8 hours for 2 consecutive nights according to standard techniques (Rechtschaffen A, Kales A, 1968) (Table 3). Following the first night in the sleep laboratory, the participants will be admitted to GCRC for a complete semi-structured medical history and physical examination. Blood, urine and saliva will be collected and an electrocardiogram (EKG) will be performed. A pregnancy test will be performed on females of child bearing age. Following the second night in the sleep laboratory, daytime sleepiness and fatigue, nighttime sleep quality and quantity, and mood will be assessed subjectively with standardized self-reported questionnaires.

b. Randomization Scheme for Intervention – Subjects will be randomly assigned by our statistician into either a trazodone or a CBT program. Between the two intervention groups, we will attempt to have similar BMI, gender, and age distributions. If a patient is randomized and enters the randomization trial, then the patient will be considered enrolled in the study.

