11.0 Statistical Analysis of the Study

Analysis

a. Sample Size Calculation – This is a pilot study to collect preliminary data using two interventions, i.e., trazodone or CBT, with unknown effects for chronic insomnia with objective short sleep duration. Based on our previous experience with interventional studies, we suggest that 10 subjects per group will be adequate to detect a difference of 20 minutes in objective sleep duration between the two treatment interventions. To allow for an anticipated 20% attrition rate, 24 subjects will be assigned to a study intervention to ensure complete data from 20 participants. The results of this study will allow the establishment of sample size for any future studies. Our statistical consultant in this study is [name].

b. Analytic Plan

Specific Aim 1: Examine the Effect of Trazodone vs. CBT for the Primary Outcome Variables (objective and subjective sleep duration) in Patients with Chronic Insomnia with Objective Short sleep Duration

Throughout the analysis, we will compare the differences (end of the interventional study baseline) between the two groups of the outcome of interest (e.g., total sleep time).

Total Sleep Time, Polysomnography: Both at baseline and the end of the intervention, polysomnography will be measured for 2 consecutive nights. We will calculate the time-specific difference from the baseline to the end of intervention. Then, we will compare the two treatment conditions with respect to the overall mean change across all time points (“difference of difference”) using the two-sample t-test. Alternatively, repeated measures analysis of variance (ANOVA) will be used to compare treatment conditions with respect to polysomnographic total sleep time changes from baseline. The time and treatment condition main effects as well as interaction between time and treatment condition will be tested. Adjustments for multiple comparisons across different time points and between intervention groups will be performed. Potential confounders and interaction between treatment condition and confounder will also be examined. In the event that the distribution of polysomnographic total sleep time are not consistent with the assumptions of normality required for ANOVA, attempts will be made to find suitable transformation.

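### If allocation is restricted on BMI, gender and age and these predict change in total sleep time, the planned unadjusted t-test is conservative; the plan does not state the allocation method

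*Combined protocol and SAP*

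**What the plan says.** Allocation (section 6.0, Randomization Scheme for Intervention): "Subjects will be randomly assigned by our statistician into either a trazodone or a CBT program". The next sentence adds: "Between the two intervention groups, we will attempt to have similar BMI, gender, and age distributions". Stratification, minimisation, blocking and category cut-points are not mentioned, so the way this similarity is to be achieved is unknown.

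Primary analysis (section 11.0, Analytic Plan, Specific Aim 1): for polysomnographic, actigraphic and diary total sleep time, the plan takes change from baseline and says "we will compare the two treatment conditions with respect to the overall mean change across all time points". The comparison is made "using the two-sample t-test. Alternatively, repeated measures analysis of variance (ANOVA) will be used to compare treatment conditions". The terms of the ANOVA are listed: "The time and treatment condition main effects as well as interaction between time and treatment condition will be tested". BMI, gender and age are in neither analysis.

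Covariates: each of the three outcome paragraphs adds "Potential confounders and interaction between treatment condition and confounder will also be examined", without naming a factor. Section 4.0 names some variables for control: family history of diabetes, and "the potential effects of other medications or substances, such as alcohol or smoking, will be controlled within our analyses". The three balancing factors are not among them.

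Prognostic value: section 4.0 explains the choice of middle-aged participants by saying that "objective sleep duration significantly correlates with age in an inverse manner". No size is given, and nothing is said about gender or BMI in relation to sleep duration.

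**The concern.** A two-sample t-test takes its standard error from the spread within arms, as if assignment had paid no attention to patient characteristics. When assignment forces the arms to be alike on factors that predict the outcome, those factors can no longer differ much between arms. The treatment difference then varies less from trial to trial than the t-test assumes, while the variation due to the factors stays in its error term. Reported intervals come out too wide and p-values too large. With only 20 completers planned, that precision is worth having if it exists, and claiming it needs only a sentence in the analysis plan.

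**Working it through.** **The plan's own figure.** Section 11.0 states 10 completers per group to detect 20 minutes. It gives no SD, alpha or power, so the figure cannot be reproduced, only inverted. For two-sided 5% and 80% power, the normal formula gives SD = 20 / [(1.960 + 0.842) × √(2/10)] = 20 / 1.253 = 16.0 minutes; with the t distribution it is 15.1. I use 15.1 below as the SD of change most favourable to the plan's claim, and 30 minutes as a less favourable value. Both are assumptions.

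**Upper bound on the effect.** Let R² be the share of variance in change explained by the three factors. With perfect balance, the true variance of the difference is (1 − R²) times what the t-test estimates, so the ratio of reported to true standard error is 1/√(1 − R²): 1.05, 1.12 and 1.20 at R² = 0.1, 0.2 and 0.3.

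**Realistic effect.** Balance in 20 patients is imperfect, so it was simulated: 10 per arm or close to it, two-sided 5%, 6,000 trials per setting, biased-coin minimisation on the three factors (probability 0.8). Minimisation and R² are both assumed. Type I error does not depend on the SD; the two figures in each cell are the runs at SD 15.1 and SD 30 and differ only by simulation error.

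| R² | Reported SE / true SE, t-test | Type I error, t-test | Power for 20 min at SD 15.1: t-test | Same, adjusted model |
|---|---|---|---|---|
| 0 | about 1.0 | 4.9%, 5.3% | 0.80 | 0.75 |
| 0.1 | 1.02 | 4.2%, 4.8% | 0.80 | 0.80 |
| 0.2 | 1.05 | 3.6%, 4.0% | 0.80 | 0.84 |
| 0.3 | 1.09 | 3.0%, 3.5% | 0.80 | 0.88 |

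The adjusted model's type I error is 5.0 to 5.2% throughout.

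**Cross-check of the type I error.** If the standard error is too large by a ratio r, the nominal 5% test rejects with probability about P(|t| > 2.101 × r) on 18 degrees of freedom. For r = 1.02, 1.05 and 1.09 this gives 4.6%, 4.1% and 3.4%, in line with the table.

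**Interval width, adjusted over unadjusted.** Multiply the ratio of mean standard errors (SD 30 runs) by the ratio of critical values on 15 and 18 degrees of freedom, 2.131/2.101 = 1.0145:

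- R² = 0: 13.79/13.27 × 1.0145 = 1.05
- R² = 0.1: 13.08/13.29 × 1.0145 = 1.00
- R² = 0.2: 12.34/13.31 × 1.0145 = 0.94
- R² = 0.3: 11.54/13.33 × 1.0145 = 0.88

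The break-even is therefore near R² = 0.1.

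**Sensitivity to the allocation method.**

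- Simple randomisation: the ratio is 0.99 to 1.02 at every R², so the t-test is correct. Adjusting then costs about 11% in width if R² = 0.
- Deterministic minimisation: 1.04, 1.08 and 1.13 at R² = 0.1, 0.2 and 0.3.
- Choosing the best balanced of 100 random allocations: 1.04–1.06, 1.11–1.12 and 1.18–1.20, close to the bound.
- Minimisation with probability 0.9, 24 allocated and 20 analysed: type I error 4.6% and 3.0% at R² = 0.2 and 0.3; adjusted interval 6% and 12% narrower, and about 6% wider at R² = 0.

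**Sensitivity to the SD.** At SD 30 and R² = 0.3, power for 20 minutes is 0.27 unadjusted and 0.35 adjusted. Adjustment helps, but does not make the trial well powered.

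**The case against.** The strongest objection is that both conditions are unproven. The protocol promises random assignment and an attempt at similar groups. A reader might infer that allocation is actively steered, but the text does not establish this, and under simple randomisation the t-test needs no correction. This objection stands and makes the point conditional.

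A reader might also take the statement about age in section 4.0 as evidence that a balancing factor predicts the primary outcome. It does not go that far. It concerns how long people sleep, while the analysis is of change, and subtracting baseline removes stable differences between people. The sample is further limited to ages 30 to 60 and under 6 hours of sleep. An R² of 0.2 to 0.3 therefore has no support in the documents; at 0 to 0.1, adjustment gains nothing or loses a little.

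Third, it would be too strong to say that the unadjusted test throws away the benefit of balance. Balance improves the estimate whatever test follows, and the t-test's power holds at about 0.80 as R² rises at SD 15.1. What is lost is recognition of that precision in the reported standard error.

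The provisions on confounders soften the point without settling it. They name none of the three factors, leave the primary t-test unchanged and do not say which result would count. Finally, a plain t-test is a defensible choice for a pilot with about 10 per arm, and any error here is on the cautious side.

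**Conclusion.** The point holds in conditional form, as a low-cost improvement. The plan intends balance on three factors and names none of them in the primary analysis. If the balance comes from restricted allocation and the factors predict change in total sleep time, the t-test's standard error is about 2 to 9% too large and its type I error about 4.5 to 3%, under assumed minimisation and an assumed R² of 0.1 to 0.3. Tighter balancing would enlarge this. If either condition fails, the t-test is valid.

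A reader might conclude that the primary test is invalid or prone to false positives. It is neither: the error, if present, makes the test conservative. The direction is certain once both conditions are met; the size rests on an allocation method and an R² that the documents do not give.

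**What to change.** State in section 6.0 how assignment achieves similarity on BMI, gender and age, or say that it is simple randomisation.

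If it is restricted, pre-specify in section 11.0, before outcome data are seen, that the primary analysis of each total-sleep-time outcome is a linear model for change with treatment and only the factors actually used in allocation, with age and BMI as continuous covariates. Keep the unadjusted t-test as supportive. If fewer factors are used in allocation, adjust for those only. If allocation is simple randomisation, this point calls for no change to the test.

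The cost is wording; age, gender and BMI have to be known for assignment in any case. The statistical price is up to 3 degrees of freedom. If none of the factors is prognostic, the interval is about 5 to 6% wider and power about 5 points lower (0.80 to 0.75 at the assumed SD of 15.1 minutes).

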clinical significance (such as the degree of objective sleep disturbance). The data on the association of objective short sleep duration in insomnia with hypercortisolemia (Vgontzas et al, 1998; Vgontzas et al, 2001; Rodenbeck et al, 2003; Rodenbeck et al, 2002; Riemann et al, 2002; Varkevisser et al, 2005) and high risk for medical morbidity (Vgontzas et al, 2009a; Vgontzas et al, 2009b; Vgontzas et al, 2010; Fernandez-Mendoza et al, 2010) provide the basis for a guided approach in the treatment of insomnia, which can be useful to the general practitioner. Because insomnia associated with objective short sleep duration is associated with HPA axis activation, the use of medication that down regulates the HPA axis, such as trazodone, may be a promising tool in the pharmacological approach. In support of this argument are the results of a small study from Germany that showed that a small dose of a sedative antidepressant (doxepin) was effective in improving sleep and normalizing plasma cortisol secretion in primary insomniacs (Rodenbeck et al, 2003). Recent studies have also shown that doxepin is effective in increasing objective sleep duration in chronic insomniacs (Rodenbeck et al, 2003; Krystal et al, 2010; Roth et al, 2010; Scharf et al, 2008; Roth et al, 2007; Hajak et al, 2001). In contrast, insomnia associated with “normal” sleep duration, normal activity of the HPA axis, and lack of significant medical morbidity may respond better to psychotherapeutic interventions. In support of this hypothesis are the several studies on CBT effectiveness that included insomniacs with an average objective sleep duration of 6 hours or more and reported improved sleep efficiency (better consolidation of sleep) but no significant lengthening of sleep duration (Edinger et al, 2001; Jacobs et al, 2004; Morin et al, 2004; Sivertsen et al, 2006a; Edinger et al, 2007a; Sivertsen et al, 2006b; Espie et al, 2007; Edinger et al, 2009; Krystal and Edinger, 2010; Okajima et al, 2010). In this project, we will focus on the more severe group and we will test whether a sedative antidepressant (trazodone) is more effective in insomnia with objective short sleep duration than CBT.

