A. Primary outcomes: we hypothesize that **trazodone** will result in a greater improvement of objective sleep duration (assessed by PSG and actigraphy) and subjective nighttime sleep than CBT in insomniacs with objective short sleep duration.

B. Secondary outcomes: we hypothesize that **trazodone** compared to CBT will result in a greater improvement of daytime fatigue, cortisol, inflammatory markers, and insulin sensitivity in insomniacs with objective short sleep duration.

The accomplishment of the above-described objectives will create the basis for the development of novel and specific treatments for chronic insomnia, and improve our understanding of the pathophysiology of this heterogeneous disorder.

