3.0 Study Design and Methods

1. Rationale – Current treatments for chronic insomnia are either partially effective and/or associated with poor outcomes in objective measures of nighttime sleep. Specifically, CBT, the most widely used therapeutic modality, is not associated with a satisfactory and clinically significant increase in objective sleep duration (Okajima et al, 2010). Furthermore, it is not known whether CBT can reverse the activation of the stress system, i.e., hypercortisolemia, associated with insomnia with objective short sleep duration. Sedative antidepressants, such as trazodone, have been shown in several studies to increase objective sleep duration and/or decrease cortisol levels (McCall, 2010). The goal of this interventional study is to assess the effect of trazodone vs. CBT in patients with chronic insomnia with objective short sleep duration.

All subjects will be randomly assigned into either a trazodone or a CBT group. The group assignment will be decided by our statistician so that the investigators

involved with subject recruitment and screening remain blind to the randomization process.

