Subjective sleep quality and insomnia severity: Both at baseline and the end of the intervention, self-reported sleep quality (PSQI) and insomnia severity (ISI) will be measured. We will calculate the time-specific difference from the baseline to the end of intervention. Then, we will compare the two treatment conditions with respect to the overall mean change across all time points (“difference of difference”) using multivariate repeated measures analysis of variance (MANOVA) to compare treatment conditions with respect to all measures of subjective sleep quality and insomnia severity changes from baseline. The time and treatment condition main effects as well as interaction between time and treatment condition will be tested. Adjustments for multiple comparisons across different time points and between intervention groups will be performed. Potential confounders and interaction between treatment condition and confounder will also be examined. In the event that the distribution of subjective sleep quality and insomnia severity measures are not consistent with the assumptions of normality required for MANOVA, attempts will be made to find suitable transformation.

Sleepiness, fatigue, and mood: Both at baseline and the end of the intervention, self-reported sleepiness (ESS), fatigue (POMS-F and MFI) and mood (BDI-II, BAI, and HAD-S) will be measured. We will calculate the time-specific difference from the baseline to the end of intervention. Then, we will compare the two treatment conditions with respect to the overall mean change across all time points (“difference of difference”) using multivariate repeated measures analysis of variance (MANOVA) to compare treatment conditions with respect to all measures of sleepiness, fatigue, and mood changes from baseline. The time and treatment condition main effects as well as interaction between time and treatment condition will be tested. Adjustments for multiple comparisons across different time points and between intervention groups will be performed. Potential confounders and interaction between treatment condition and confounder will also be examined. In the event that the distribution of sleepiness, fatigue, and mood measures are not consistent with the assumptions of normality required for MANOVA, attempts will be made to find suitable transformation.

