Stress, inflammation, and insulin sensitivity: Both at baseline and the end of the intervention, saliva cortisol, TNF α , TNFr1, IL-6, and the fasting glucose to insulin ratio (G/I) will be measured. We will calculate the time-specific difference from the baseline to the end of intervention. Then, we will compare the two treatment conditions with respect to the overall mean change across all time points (“difference of difference”)

using multivariate repeated measures analysis of variance (MANOVA) to compare treatment conditions with respect to all measures of stress, inflammation and insulin sensitivity changes from baseline. The time and treatment condition main effects as well as interaction between time and treatment condition will be tested. Adjustments for multiple comparisons across different time points and between intervention groups will be performed. Potential confounders and interaction between treatment condition and confounder will also be examined. In the event that the distribution of stress, inflammation and insulin sensitivity measures are not consistent with the assumptions of normality required for MANOVA, attempts will be made to find suitable transformation.

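### The pooled MANOVAs named for the secondary outcomes do not attribute a treatment difference to fatigue, cortisol, a cytokine marker or insulin sensitivity, as the stated hypothesis requires

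*Combined protocol and SAP*

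**What the plan says.** Section 2.0, item B, predicts that trazodone will give a "greater improvement of daytime fatigue, cortisol, inflammatory markers, and insulin sensitivity" than CBT. Cortisol also carries the mechanistic rationale. Section 1.0 D argues that "the use of medication that down regulates the HPA axis, such as trazodone, may be a promising tool in the pharmacological approach". Section 3.0 adds that "it is not known whether CBT can reverse the activation of the stress system, i.e., hypercortisolemia", and reports that sedative antidepressants have been shown to "increase objective sleep duration and/or decrease cortisol levels".

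Section 11.0 b, Specific Aim 2, analyses these outcomes in groups:

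- **Fatigue.** POMS-F and MFI enter one MANOVA with ESS, BDI-II, BAI and HAD-S, to "compare treatment conditions with respect to all measures of sleepiness, fatigue, and mood changes from baseline".
- **Biomarkers.** Salivary cortisol, TNF-alpha, TNFr1, IL-6 and the fasting glucose/insulin ratio (G/I) enter another, to "compare treatment conditions with respect to all measures of stress, inflammation and insulin sensitivity changes from baseline".

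In each case the plan calculates changes from baseline and will "compare the two treatment conditions with respect to the overall mean change across all time points". It tests treatment, time and their interaction, and states: "Adjustments for multiple comparisons across different time points and between intervention groups will be performed".

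Under Specific Aim 1, by contrast, sleep time by polysomnography, actigraphy and diary each has its own t-test or ANOVA.

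**The concern.** The hypothesis is a list of separate predictions, each with a direction. The named test asks one question per group: do the arms differ on some combination of these measures? A yes does not say which measure is responsible.

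This matters in two places. In the fatigue group, four of the six scales lie outside the Section 2.0 hypothesis, so a mood effect alone can make the test significant. In the biomarker group, a difference in one cytokine marker can produce a significant result that says nothing about cortisol.

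Investigators would then look measure by measure with no stated rule for multiplicity or for what counts as improvement. Section 11.0 also says that the results will set the sample size of later studies. That needs a difference and an SD per outcome, which a MANOVA p-value does not supply.

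**Working it through.** **Inputs from the plan.** Section 11.0 expects 10 evaluable patients per arm. Its enrolment figure reproduces as 20 × 1.20 = 24 (24 × 0.80 gives 19.2 expected completers); only the 10 per arm is used below. The plan gives no alpha, sidedness, SD or correlation for the secondary outcomes.

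**Assumptions.** Two-sided 0.05; shifts of 0.8 SD of change; equal correlation ρ between measures of 0, 0.3 or 0.5; one score per scale; biomarkers averaged over a visit's samples.

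**Formula.** For two arms the MANOVA treatment test is Hotelling's T², with F on p and 19 − p degrees of freedom and noncentrality

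λ = (10/2) × [Σδ² − ρ(Σδ)²/(1 + (p − 1)ρ)]/(1 − ρ).

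**Six-scale MANOVA** (p = 6, critical F(6,13) = 2.915). With only the three mood scales shifted, Σδ² = 1.92 and Σδ = 2.4. At ρ = 0.3, λ = 5 × (1.92 − 0.12 × 5.76)/0.7 = 8.78. With only the two fatigue scales shifted, Σδ² = 1.28 and Σδ = 1.6. At ρ = 0.3, λ = 5 × (1.28 − 0.12 × 2.56)/0.7 = 6.95.

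| What truly differs | λ at ρ = 0 / 0.3 / 0.5 | Significant |
|---|---|---|
| Three mood scales only | 9.60 / 8.78 / 10.97 | 42 / 38 / 47% |
| Two fatigue scales only | 6.40 / 6.95 / 9.14 | 28 / 30 / 40% |

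At each of these correlations the test responds more often to a pattern outside the hypothesis than to the hypothesised one.

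**Five-biomarker MANOVA** (p = 5, critical F(5,14) = 2.958). If all five improve by 0.8 SD, λ = 16.0 / 7.27 / 5.33 and power is 72 / 37 / 27%. It is identical if all five worsen. If three improve and two worsen, power is 72 / 87 / 96%. If only TNFr1 differs, by 1.5 SD, the test is significant in about 55 / 66 / 80% of simulated trials. Cortisol on its own significantly favours trazodone in about 3% of those.

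**Separate tests.** Simulation with 40,000 trials per setting, a baseline to month-3 correlation of 0.5 (assumed), and Holm over 2 fatigue or 5 biomarker tests. A success is at least one significant improvement.

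| True pattern | MANOVA | ANCOVA with Holm | Change-score t-tests with Holm |
|---|---|---|---|
| Both fatigue scales improve | 28 / 30 / 40% | about 58 / 55 / 52% | about 48 / 46 / 42% |
| All five biomarkers improve | 72 / 37 / 27% | about 72 / 63 / 55% | about 61 / 52 / 45% |

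When only mood moves, Holm-adjusted ANCOVAs on POMS-F and MFI falsely show a fatigue improvement in about 2.5% of trials. With all five biomarkers improved, ANCOVA with Holm detects each single marker in only 26–28%.

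**The case against.** A reader might infer that the plan cannot show greater improvement at all, or that the direction of effect is lost. The documents do not support that. Signed changes from baseline are calculated and compared between arms, so direction can be read descriptively. A two-sided test of a single measure also rejects equally in either direction, with its sign read from the estimate. What is missing is attribution and a planned inference per outcome.

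Nor is each MANOVA a single test: treatment, time and interaction are all examined. None of these is stated per measure, however, so the attribution gap remains.

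A reader might also infer a large gain in power from separate tests. That needs qualifying, because moving to Holm-adjusted ANCOVAs changes the set of scales, the type of test and the baseline adjustment together. With the plan's own change scores, the fatigue result at correlation 0.5 is about 42%, against 40% for the MANOVA. For the biomarkers at correlation 0, change-score tests do worse than the MANOVA (about 61% against 72%) and ANCOVA only ties it.

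Finally, this is a pilot, and the 10 per group was justified only for objective sleep duration. That limits the priority. It does not remove the point, since a pilot meant to inform later sample sizes needs estimates per outcome.

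**Conclusion.** The concern holds in this form: the only inference named for the Section 2.0 secondary hypothesis is a pooled MANOVA. It does not attribute a difference to any hypothesised outcome, and the adjustment rule leaves multiplicity across measures open.

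The clearest sign of the mismatch is the six-scale test, significant in 42/38/47% of trials for a mood-only effect and in 28/30/40% for a fatigue-only effect. These figures rest on the assumed 0.8 SD shifts, equal correlations and 10 per arm. The lack of attribution does not depend on them.

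Priority is modest. The benefit of changing is mainly attribution and an estimate per outcome; part of the power gain comes from baseline adjustment, and single-marker power stays low.

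**What to change.** For each outcome in the Section 2.0 secondary hypothesis (POMS-F, MFI, cortisol, TNF-alpha, TNFr1, IL-6 and G/I):

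- Make the main secondary analysis a separate ANCOVA of the month-3 value on treatment and baseline. Report the between-arm difference, its 95% CI and the SD.
- For cortisol and the cytokine markers, use the mean over the visit's samples and keep the within-day pattern as a supportive analysis; Section 6.0 takes repeated samples because levels vary over the day. For G/I, use only the morning fasting sample, because Section 6.0 collects both evening and morning blood.
- State beforehand what counts as improvement: lower fatigue scores, cortisol and cytokine markers, and higher G/I. The plan gives no signs for most of these, so the investigators should confirm them.
- Apply Holm within the fatigue family (2 tests) and within the biomarker family (5 tests).
- Keep the MANOVAs as supportive analyses.

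The cost is wording only: samples, assays, questionnaires and visits stay the same. Each model spends one degree of freedom (18 to 17). Seven tests in two families carry up to 1 − 0.95² = 9.8% chance of at least one false claim overall, if the families are independent. With 20 completers, the intervals will be more useful than the significance tests.
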